9.1 Definitions

9.1.1 Adverse Event

An adverse event is defined as any untoward medical occurrence in a patient or clinical investigation subject administered a pharmaceutical product and which does not necessarily have to have a causal relationship with this treatment. An adverse event can therefore be any unfavorable and unintended sign (including an abnormal laboratory finding or vital sign which requires protocol treatment to be modified, for example), symptom, or disease temporally associated with the use of a medicinal product or protocol-specified procedure, whether or not considered related to the medicinal product or protocol-specified procedure. Any worsening (i.e., any clinically significant adverse change in frequency and/or intensity) of a preexisting condition that is temporally associated with the use of the study drugs, is also an adverse event.

Progression of the cancer under study and/or symptoms related to progression of the underlying cancer are not considered an adverse event.

9.1.2 Serious Adverse Event

An adverse event is considered “serious” if, in the view of the investigator it results in any of the following outcomes:

- Death

If death results from (progression of) the disease, the disease should be reported as event (SAE) itself.

- A life-threatening adverse event

An adverse event is considered ‘life-threatening’ if, in the view of either the investigator or sponsors, its occurrence places the patient or subject at immediate risk of death. It does not include an adverse event that, had it occurred in a more severe form, might have caused death.

- Inpatient hospitalization or prolongation of existing hospitalization for ≥ 24 hours.
- A persistent or significant incapacity or substantial disruption of the ability to conduct normal life functions
- A congenital anomaly/birth defect

- Important medical event: Any event that may not result in death, be life-threatening, or require hospitalization may be considered serious when, based upon appropriate medical judgment, they may jeopardize the patient and may require medical or surgical intervention to prevent one of the outcomes listed in this definition of “Serious Adverse Event”. Examples of such medical events include allergic bronchospasm requiring intensive treatment in an emergency room or at home; convulsions that do not result in inpatient hospitalization or the development of drug dependency or drug abuse.

9.1.3 Expected Adverse Events

An adverse event (AE) is considered “expected” if:

- For approved and marketed drugs, those adverse events are described in the approved Package Insert.

9.1.4 Events Not Qualifying as SAEs

Previously planned (prior to signing the informed consent form) surgeries should not be reported as SAEs unless the underlying medical condition has worsened during the course of the study. Preplanned hospitalizations or procedures for preexisting conditions that are already recorded in the patient’s medical history at the time of study enrollment should not be considered SAEs. Hospitalization or prolongation of hospitalization without a precipitating clinical AE (for example, for the administration of study therapy or other protocol-required procedure) should not be considered SAEs. However, if the preexisting condition worsened during the course of the study, it should be reported as an SAE. *Progression of the cancer under study and/or symptoms related to progression of the underlying cancer are not considered a serious adverse event unless it resulted in death.*

9.2 Evaluating Adverse Events

An investigator who is a qualified physician will evaluate all adverse events according to the NCI Common Terminology for Adverse Events (CTCAE), version 4.0.3 All appropriate treatment areas should have access to a copy of the CTCAE version 4.03. A copy of the CTCAE version 4.03 can be downloaded from the CTEP web site. (https://evs.nci.nih.gov/ftp1/CTCAE/CTCAE_4.03_2010-06-14_QuickReference_8.5x11.pdf) Any adverse event which changes CTCAE grade over the course of a given episode will have each change of grade recorded.

All adverse events regardless of CTCAE grade must also be evaluated for seriousness.

Attribution of the AE

The investigator or co-investigator is responsible for assignment of attribution.

Definite – The AE *is clearly related* to the study treatment.

Probable – The AE *is likely related* to the study treatment.

Possible – The AE *may be related* to the study treatment.

Unlikely – The AE *is doubtfully related* to the study treatment.

Unrelated – The AE *is clearly NOT related* to the study treatment/intervention

9.3 Reporting of Adverse Events

9.3.1 Reporting procedures for multi-site trials

All adverse events (AEs), serious adverse events (SAEs) and unanticipated problems (UPs), will be reported to the IRB per current institutional standards.

10.0 CORRELATIVE STUDIES

10.1 FDG-PET: [¹⁸F]-fluorodeoxyglucose (FDG) has been used extensively as a glucose analogue to image glycolysis in the body. It accumulates in many cancers, most notably lung cancer due to their elevated glycolytic rate compared to normal background tissue. This has allowed FDG to be the standard for oncologic staging prior to therapy, and one of the main modalities to monitor recurrent disease/treatment response to therapy. In FDG PET/CT, significant variation in tracer uptake has been suggested to be 30 % for the SUV max using PERCIST criteria (34) Although this metric has been suggested, we will also look at normalized SUV max using an internal reference tissue given that tumor burden and hyperglycemia has been shown to effect PERCIST criteria (35, 36) Additionally, total lesion glycolysis (the SUV mean of the segmented volume multiplied by the tumor volume) has been shown to be a better estimation of FDG uptake and account for variation of a very “hot tumor” that is small compared to a “warm tumor” that is large (35)

10.2 FLT-PET: [¹⁸F]-3-fluoro-deoxy-thymidine (FLT) is a thymidine analogue as FDG is an analogue to glucose. It is an NIH held IND drug with a current/active RDRC at the University of Michigan. FLT’s incorporation into the cell occurs through thymidine kinase within the DNA synthesis machinery. Once in the cell it is phosphorylated and trapped within the cytosol. The degree of uptake correlates to the degree of DNA synthesis/proliferation, analogous to Ki-67. FLT PET/CT imaging will be used both prior to and after DEX treatment (37). The initial scan will provide a baseline DNA synthesis rate based on the uptake within the tumor. Following DEX therapy, if there is senescence as predicted and resultant G1 arrest, there will be fewer cells in S phase (DNA synthesis) and a corresponding reduction in FLT uptake in the tumor. The reduction in FLPET is hypothesized to be directly proportional to reduced FDG uptake, denoting response to therapy. FLT PET can eventually be used a biomarker to identify who would benefit from the proposed approach in this study.

10.3 GR expression

A specific cut-off for tumoral GR expression is not a pre-requisite for enrollment onto this protocol. Tumoral GR expression will be determined by immunohistochemistry (IHC) methods. GR expression will be divided as low (<1%), intermediate (1-49%), and high (\geq 50%).

10.4 SASP

The tumor cells will remain senescent and continue secreting SASP even after Dex washout. The SASP is expected to enhance the frequency and cytolytic functions of T and NK cells in the peripheral blood as well as in the tumor, especially in combination with the checkpoint inhibitor, Pembrolizumab. The SASP will be analyzed by a multiplex cytokine array

10.5 T and NK cells in PBMC

T cells and NK cells are major contributors to cytolytic function against the tumor, which is often blocked by PD1-PDL1 interaction. Although the number of T cells would deplete to some extent during Dex treatment, it is expected to recover quickly during/following the 3-day washout., while a multi-parametric flow cytometric analysis will detect any change in the number and functions of T and NK cells in the peripheral blood.

11.0 STATISTICAL ANALYSIS PLAN

11.1 Statistical Design (see page 10 for Schema)

In the first stage, three DEX escalation cohorts will be evaluated sequentially from Cohort A to Cohort C until two or more patients have the FLT-PET response (i.e., \geq 30% reduction in FLT-PET uptake in at least one target lesion) and, otherwise, the trial will be terminated due to futility. When a lead-in cohort has two or more FLT-PET responses, this lead-in cohort will be considered the optimal DEX duration and the primary endpoint will be evaluated in the following second and third stages using this optimal DEX duration. That is, after the optimal DEX duration is decided in the first stage, six additional patients will be enrolled in the second stage with the same DEX duration as the associated cohort. If four or less patients respond among 11 patients, the trial will be terminated. Otherwise, 10 additional patients will be enrolled in the third stage. The null hypothesis ($p_0 = 30\%$) will be rejected if 10 or more FLT-PET responses are observed in 21 patients. This design yields a 1-sided type I error rate of 5% and power of 80% when the true FLT-PET response rate is 60% (i.e., $p_1 = 60\%$). The minimum sample size will be 11 patients when Cohort A becomes the optimal duration and the trial is terminated at the end of the second stage. The maximum sample size will be 31 patients when Cohort C becomes the optimal duration and the patients are enrolled into the third stage.

We will also explore the associations between the FLT-PET response and the changes in senescence associated secretory proteins (SASP) and lymphocyte, phenotypic and functional markers (LPFM), (ii) monitor the changes and trajectories in SASP and LPFM, and (iii) explore the association between the FLT-PET response and GR expression at cycle 0. The expression levels of SASP and LPFM/GR will be measured using plasma and tissue samples,

respectively. The secondary endpoints are the changes in SASP and LPFM expression levels between cycle 0 and cycle 1 as well as the expression level of GR at cycle 0. The association between the FLT-PET response and the changes in the expression levels of each of SASP and LPFM will be examined using logistic regression models. The expression levels of SASP and LPFM between cycle 0 and cycle 1 will be examined using a paired t-test, if needed, after data transformation (such as log or square root transformation). The association between the FLT-PET response and the GR expression level will be assessed using logistic regression models. The trajectories from cycle 0 to cycle 4 for the expression levels of each of SASP and LPFM will be examined to see if the expression levels increase monotonically across cycles. To do this, linear mixed-effects models will be used, if needed, after data transformation. In addition, in case that either Cohort B or C becomes the optimal duration, we will descriptively compare the changes in SASP and LPFM expression levels from cycle 0 to cycle 1 between lead-in cohorts. Because these are a discovery study to generate hypotheses, no multiple comparison correction will be made. However, if either the sample size is less than 12 patients or a level (i.e., response vs. non-response) has less than 5 events; all secondary objectives will be exploratory and will be summarized descriptively. All statistical analyses will be based on complete data and no missing data analysis will be performed.

The secondary objective is to assess the effect of DEX on pembrolizumab in terms of overall response rate (ORR), which is the primary endpoint. Based on our previous pre-clinical and clinical studies, we hypothesize that the true ORR of DEX followed by pembrolizumab will be at least 33% (i.e., $p_1 = 0.33$) vs. the historical control whose ORR is at most 7% (i.e., $p_0 = 0.07$). The ORR will be statistically evaluated when the FLT-PET response trial enters the third stage, where the number of patients with the selected optimal DEX duration will be 21. Otherwise, the ORR will be summarized descriptively. The null hypothesis ($p_0 = 7\%$) will be rejected if five or more responses are observed in 21 patients, which yields a 1-sided type I error rate of 5% and power of 87% when the true ORR is 33% (i.e., $p_1 = 33\%$).

We will also to explore the associations between ORR and the changes in expression levels of each of SASP and LPFM from cycle 0 to cycle 1, (ii) to explore the association between ORR and GR expression at cycle 0, and (iii) to explore the progression-free survival (PFS). The associations between ORR and the changes of SASP and LPFM and between ORR and the GR expression will be examined using logistic regression models and no multiple comparison correction will be made because these are a discovery study to generate hypotheses. The distribution of PFS will be summarized graphically using the Kaplan-Meier (KM) curve and the median PFS and associated 95% confidence interval will be estimated using KM estimate. If either the sample size is less than 12 patients or a level (i.e., response vs. non-response) has less than 5 events, the secondary objectives will be exploratory and will be summarized descriptively. All statistical analyses will be based on complete data and no missing data analysis will be performed.

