2.0 TRIAL DESIGN

2.1 Trial Design

This study is a small Phase II clinical trial designed as a single-arm two-stage study with Dexamethasone dose escalation cohorts (4mg BID on days 1-7, 1-10 or 1-13). The trial will include FLT-PET and FDG-PET imaging to measure tumor senescence to Dexamethasone and treatment response respectively, and also blood analysis for SASP and markers of immune activation. This study is to assess whether senescence induced by oral dexamethasone resensitizes NSCLC patients to intravenous pembrolizumab.

We will use a single arm phase II two-stage design with 3 Dex cohorts (4 mg bid, on Days 1-7, 1-10 and 1-14) to achieve 80% power at a 1-sided alpha 10% level. Each cohort will consist of 5 patients. On the basis of Simon's optimal design, the first cohort will be accrued in the first stage. If there are 3 or more "responses" occur among this cohort, 7 additional patients will be accrued and treated with the same Dex dose for a total of 12 patients; if 7 or more respond at this dose level, we will add 9 more patients for a total of 21 patients (with 20% drop out, n = 31). If no response is noted on FLTPET, 2nd cohort will open up with a 10 day fixed dose Dex and so on as depicted in Schema.

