6.3 Dexamethasone dose modification: CBC and Metabolic profile will be monitored once weekly while on DEX. Any Grade III or greater non-hematological side effect will result in holding the DEX with resumption only when AE is Grade 1 or lower, and patient is asymptomatic. If symptomatic, DEX will be permanently discontinued.

6.4 Diet/Activity/Other Considerations: No special considerations. In diabetics, we will encourage stricter adherence to sugar free meals

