7.2 Treatment Calendar

SCHEDULE OF EVENTS COHORT 1

Procedure	Screening (within 28 days prior to Day 0) ¹	Baseline Day 0	(C1D1)	Lead In C2 and C3	(C2 and 3D1) (± 3Days)	(C4+) (± 3 Days)	EOT	Follow Up ¹
Informed Consent	X							
Medical History	X							
Physical exam	X		X		X	X	X	
Vital Signs	X		X		X	X	X	
ECOG performance status	X		X		X	X	X	
Adverse Events	X		X		X	X	X	X
Concomitant Medications	X		X		X	X	X	X
CBCPD	X		X		X	X	X	
Comp	X		X		X	X	X	
Coagulation (PT/aPTT) ⁷	X							
FDG PET/CT-Chest (VA Ann Arbor) ²	X					X	X	
CT Abdomen/Pelvis ³	X							
Research Blood ⁴		X	X		X			
FLT PET (University of Michigan)		X	X					
Dexamethasone ⁵		X		X	X			
Pembrolizumab ⁶			X		X	X		

¹ Follow Up: Phone call 6 weeks after EOT including any new treatments

² FDG PET/CT-Chest: C4D1 (±7days), then Every 12 weeks (±7days)

³ CT-Abdomen/Pelvis: at screening, C4D1 (±7days), then Every 12 weeks (±7days) **only if disease is present in that area**

⁴ Research Blood: T/TK, SAP, cytokines, chemokines, immune cell subsets; Drawn with 1st FLT PET, 2nd FLT PET, C1D1, C2D1, C3D1 only

⁵ Dexamethasone given orally. Start immediately after FLT PET Day 0 – Day 9. Lead in Day 9-17

⁶ Pembrolizumab given up to 1 year every 21 days

⁷ Only required if clinically indicated or on anticoagulants

SCHEDULE OF EVENTS COHORT 2

Procedure	Screening (within 28 days prior to Day 0) ¹	Baseline Day 0	(C1D1)	Lead In C2 and C3	(C2 and 3D1) (± 3Days)	(C4+) (± 3 Days)	EOT	Follow Up ¹
Informed Consent	X							
Medical History	X							
Physical exam	X		X		X	X	X	
Vital Signs	X		X		X	X	X	
ECOG performance status	X		X		X	X	X	
Adverse Events	X		X		X	X	X	X
Concomitant Medications	X		X		X	X	X	X
CBCPD	X		X		X	X	X	
Comp	X		X		X	X	X	
Coagulation (PT/aPTT) ⁷	X							
FDG PET/CT-Chest (VA Ann Arbor) ²	X					X	X	
CT Abdomen/Pelvis ³	X							
Research Blood ⁴		X	X		X			
FLT PET (University of Michigan)		X	X					
Dexamethasone ⁵		X		X	X			
Pembrolizumab ⁶			X		X	X		

¹ Follow Up: Phone call 6 weeks after EOT including any new treatments

² FDG PET/CT-Chest: C4D1 (±7days), then Every 12 weeks (±7days)

³ CT-Abdomen/Pelvis: at screening, C4D1 (±7days), then Every 12 weeks (±7days) **only if disease is present in that area**

⁴Research Blood: T/TK, SAP, cytokines, chemokines, immune cell subsets; Drawn with 1st FLT PET, 2nd FLT PET, C1D1, C2D1, C3D1 only

⁵ Dexamethasone given orally. Start immediately after FLT PET Day 0 – Day 9. Lead in Day 9-17

⁶Pembrolizumab given up to 1 year every 21 days

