⁷Only required if clinically indicated or on anticoagulants

SCHEDULE OF EVENTS COHORT 3

Procedure	Screening (within 28 days prior to Day 0) ¹	Baseline Day 0	(C1D1)	Lead In C2 and C3	(C2 and 3D1) (± 3Days)	(C4+) (± 3 Days)	EOT	Follow Up ¹
Informed Consent	X							
Medical History	X							
Physical exam	X		X		X	X	X	
Vital Signs	X		X		X	X	X	
ECOG performance status	X		X		X	X	X	
Adverse Events	X		X		X	X	X	X
Concomitant Medications	X		X		X	X	X	X
CBCPD	X		X		X	X	X	
Comp	X		X		X	X	X	
Coagulation (PT/aPTT) ⁷	X							
FDG PET/CT-Chest (VA Ann Arbor) ²	X					X	X	
CT Abdomen/Pelvis ³	X							
Research Blood ⁴		X	X		X			
FLT PET (University of		X	X					
Dexamethasone ⁵		X		X	X			
Pembrolizumab ⁶			X		X	X		

¹ Follow Up: Phone call 6 weeks after EOT including any new treatments

² FDG PET/CT-Chest: C4D1 (±7days), then Every 12 weeks (±7days)

³ CT-Abdomen/Pelvis: at screening, C4D1 (±7days), then Every 12 weeks (±7days) **only if disease is present in that area**

⁴ Research Blood: T/TK, SAP, cytokines, chemokines, immune cell subsets; Drawn with 1st FLT PET, 2nd FLT PET, C1D1, C2D1, C3D1 only

⁵ Dexamethasone given orally. Start immediately after FLT PET Day 0 – Day 9. Lead in Day 9-17

⁶ Pembrolizumab given up to 1 year every 21 days

⁷ Only required if clinically indicated or on anticoagulants

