35	Tu	AM	PM	____ mg AM	____ mg PM		
36	W	AM	PM	____ mg AM	____ mg PM		
37	Th	AM	PM	____ mg AM	____ mg PM		
38	F	AM	PM	____ mg AM	____ mg PM		
39	Sa	AM	PM	____ mg AM	____ mg PM		
40	Su	No Dexamethasone					
41	M	No Dexamethasone					
42	Tu	No Dexamethasone					
43	W	Blood Draw; RV w/[name] @ _____; PEMBROLIZUMAB INFUSION (Cycle 3 Day 1 =3rd Dose)					

IVC. PATIENT'S MEDICATION DIARY COHORT 3 CYCLE 1 – 3Today's date _____ Agent: **Dexamethasone**

Patient Initials _____ Patient Study ID _____

INSTRUCTIONS TO THE PATIENT:-

- You will take **Dexamethasone orally twice a day, approximately 12 hours apart**
- You should take your capsule(s) at approximately the same time each morning and evening.

Dexamethasone Taper

4mg Dex morning and evenings on Days 9-21; then again on Days 37-49

2mg Dex morning and evenings on Days 22-24; then again on Days 50-52

1mg Dex morning and evenings on Day 25; then again on Day 53

Day	Date	Time of Dose		Dexamethasone		Comments	
		AM	PM	_____ mg	_____ mg		
	TH	FLT PET @ UM @ _____; Blood Draw; Start Dexamethasone					
		AM	PM	_____ mg AM	_____ mg PM		
	F	AM	PM	_____ mg AM	_____ mg PM		
	Sa	AM	PM	_____ mg AM	_____ mg PM		
	Su	AM	PM	_____ mg AM	_____ mg PM		
	M	AM	PM	_____ mg AM	_____ mg PM		
	Tu	AM	PM	_____ mg AM	_____ mg PM		
	W	AM	PM	_____ mg AM	_____ mg PM		
	Th	AM	PM	_____ mg AM	_____ mg PM		
	F	AM	PM	_____ mg AM	_____ mg PM		
	Sa	AM	PM	_____ mg AM	_____ mg PM		
	Su	AM	PM	_____ mg AM	_____ mg PM		
	M	AM	PM	_____ mg AM	_____ mg PM		
	Tu	AM	PM	_____ mg AM	_____ mg PM		
	W	AM	PM	_____ mg AM	_____ mg PM		
	Th	AM	PM	_____ mg AM	_____ mg PM		
	F	AM	PM	_____ mg AM	_____ mg PM		
	Sa	AM	PM	_____ mg AM	_____ mg PM		
	Su	No Dexamethasone					
	M	No Dexamethasone					
	Tu	No Dexamethasone					
1	W	FLT PET @ UM @ _____; Blood Draw; RV w/[name] @ _____;					
		PEMBROLIZUMAB INFUSION (Cycle 1 Day 1 = 1st Dose)					
2	Th						

3	F						
4	Sa						
5	Su						
6	M						
7	Tu						
8	W						
9	Th	AM	PM	____ mg AM	____ mg PM		
10	F	AM	PM	____ mg AM	____ mg PM		
11	Sa	AM	PM	____ mg AM	____ mg PM		
12	Su	AM	PM	____ mg AM	____ mg PM		
13	M	AM	PM	____ mg AM	____ mg PM		
14	Tu	AM	PM	____ mg AM	____ mg PM		
15	W	AM	PM	____ mg AM	____ mg PM		
16	Th	AM	PM	____ mg AM	____ mg PM		
17	F	AM	PM	____ mg AM	____ mg PM		
18	Sa	AM	PM	____ mg AM	____ mg PM		
19	Su	AM	PM	____ mg AM	____ mg PM		
20	M	AM	PM	____ mg AM	____ mg PM		
21	Tu	AM	PM	____ mg AM	____ mg PM		
22	W	AM	PM	____ mg AM	____ mg PM		
23	Th	AM	PM	____ mg AM	____ mg PM		

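### The 7.2 calendars schedule none of the weekly labs that 6.3 requires during dexamethasone, and their footnote 5 gives dosing days that fit no cohort

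*Combined protocol and SAP*

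**What the plan says.** Section 6.3 sets the monitoring rule, "CBC and Metabolic profile will be monitored once weekly while on DEX", and the action that depends on it: "Any Grade III or greater non-hematological side effect will result in holding the DEX". DEX resumes only when the event is back to Grade 1 or lower. Section 6.4 expects diabetic patients: "In diabetics, we will encourage stricter adherence to sugar free meals".

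Section 7.2 gives one schedule of events per cohort. In all three, the CBC and metabolic panel rows are marked at screening, C1D1, C2D1/C3D1, C4+ and end of treatment. Both rows are blank at Baseline Day 0 and in the column headed "Lead In C2 and C3". DEX is marked in those two columns and also at C2D1/C3D1.

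Footnote 5 is identical in the three schedules. It runs the first course from Day 0 to Day 9 and adds "Lead in Day 9-17".

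Section 6.1 and the diaries in Appendix IV give different courses by cohort, each followed by three days without DEX before pembrolizumab. For cohort 3 the diary reads: "4mg Dex morning and evenings on Days 9-21; then again on Days 37-49", followed by a four-day taper.

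Section 11.1 then carries one duration forward: "When a lead-in cohort has two or more FLT-PET responses, this lead-in cohort will be considered the optimal DEX duration". Six and then ten more patients may be treated at that duration, on that cohort's calendar.

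**The concern.** Visits and draws are normally booked from the schedule of events. Staff who follow it would draw no CBC or metabolic profile while a patient is taking DEX. The Grade 3 hold in 6.3 could then miss events that only a lab detects. Hyperglycemia is the obvious one: section 4.1 lists it among the effects of long-term DEX, 6.4 expects diabetics, and 5.2 does not exclude them.

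Footnote 5 raises a second problem. Duration of DEX is what separates the cohorts and what 11.1 selects. If anyone dosed from the footnote, cohorts 2 and 3 would receive shorter courses than 6.1 defines, and a duration could be called optimal that was not the one delivered.

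**Working it through.** **Inputs.** Course lengths and wash-out come from 6.1. Dosing days and visit days come from the Appendix IV diaries. Lab marks, the ±3-day window (C2D1/C3D1 and C4+) and footnote 5 come from 7.2. Section 6.1 gives no day count for the last taper step in cohort 1; the diary gives one day.

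**Step 1. Reproduce the diary days.** Course = full-dose days + taper days. Next pembrolizumab day = last DEX day + 3 wash-out days + 1.

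| | Cohort 1 | Cohort 2 | Cohort 3 |
|---|---|---|---|
| Course (days) | 7 + 2 = 9 | 10 + 3 = 13 | 13 + 4 = 17 |
| DEX before C2D1 | Days 10–18 | Days 6–18 | Days 9–25 |
| C2D1 | 18 + 4 = 22 | 18 + 4 = 22 | 25 + 4 = 29 |
| DEX before C3D1 | Days 31–39 | Days 27–39 | Days 37–53 |
| C3D1 | 39 + 4 = 43 | 39 + 4 = 43 | 53 + 4 = 57 |

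These match the visit days printed in the diaries.

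**Step 2. Does any scheduled lab fall on a DEX day?** Take C2D1 and C3D1 at their earliest, 3 days early:

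- Cohorts 1 and 2: 22 − 3 = Day 19 (last DEX Day 18) and 43 − 3 = Day 40 (last DEX Day 39).
- Cohort 3: 29 − 3 = Day 26 (last DEX Day 25) and 57 − 3 = Day 54 (last DEX Day 53).

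Each is the first day without DEX. For the first course, C1D1 comes 9 + 3 = 12, 13 + 3 = 16 or 17 + 3 = 20 days after the first dose, which is 4 days after the last one. Screening precedes DEX, and C4+ follows the third and last course.

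**Step 3. Compare with 6.3.** Count completed weeks per course, then multiply by three courses.

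| | Cohort 1 | Cohort 2 | Cohort 3 |
|---|---|---|---|
| DEX days, three courses | 3 × 9 = 27 | 3 × 13 = 39 | 3 × 17 = 51 |
| Labs scheduled on DEX days | 0 | 0 | 0 |
| Labs implied by 6.3, at least | 3 × 1 = 3 | 3 × 1 = 3 | 3 × 2 = 6 |
| Counting part-weeks as weeks | 3 × 2 = 6 | 3 × 2 = 6 | 3 × 3 = 9 |

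**Step 4. Check footnote 5.** Counted inclusively, Day 0 to Day 9 is 10 days and Day 9 to Day 17 is 9 days.

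| | Cohort 1 | Cohort 2 | Cohort 3 |
|---|---|---|---|
| First course, 6.1 and diary | Days 0–8 | Days 0–12 | Days 0–16 |
| Footnote (0–9) differs by | 10 − 9 = +1 day | 10 − 13 = −3 days | 10 − 17 = −7 days |
| Later courses, diary | Days 10–18 | Days 6–18 | Days 9–25 |
| Footnote (9–17) differs by | same length, one day early | 9 − 13 = −4 days | 9 − 17 = −8 days |
| Three courses as footnoted (10 + 9 + 9 = 28) | 28 v 27 | 28 v 39 | 28 v 51 |

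The footnote fits no cohort exactly. It is close for cohort 1, and taken literally it would be 11 and 23 days short in cohorts 2 and 3.

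**The case against.** The best defense is that 6.3 is binding and the calendar only summarizes. Section 7.1 describes the schedule as a summary and allows unscheduled procedures. That stands: the protocol does require lab monitoring on DEX, and a reader should not infer that it has none. But the 7.1 allowance covers procedures the investigator judges necessary, whereas the 6.3 draw is mandatory. A mandatory weekly draw belongs where visits are booked.

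Patients also dose from the diaries, which carry the right days. So the shortfall from footnote 5 is a risk if the footnote is followed, not a prediction.

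The gap between labs could be made to look larger. Adding the 28-day screening window gives 40, 44 or 48 days. Up to 28 of those days precede any DEX, so 12, 16 and 20 days are the relevant figures.

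A further inference is tempting: that the cohort steps are unsafe because they turn on FLT-PET counts alone. In 2.1, for example, "If no response is noted on FLTPET, 2nd cohort will open up with a 10 day fixed dose Dex"; 11.1 works in the same way. The documents do not support calling this a fault.

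- Section 6.3 holds DEX in the individual patient, 6.6 item 3 can end the trial on adverse reactions, and the DSMC in 13.4 meets monthly on safety. Figure 1 is not shown and may hold a gate.
- Section 4.2.2 says no phase I data exist for this pre-treatment, but it also reports no apparent overlap in serious events between the two drugs.
- The documents give no toxicity rate, so any numeric limit is a judgment. For example, at an assumed 30% rate, pausing at 3 of 5 or 5 of 11 would trigger 27% of the time. Pausing at 2 of 5 or 4 of 11 would trigger 58% of the time, but also 31% at an assumed 20% rate.

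Reasonable statisticians would differ on adding such a limit.

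**Conclusion.** The schedule conflict holds. As written, the three calendars place 0 safety labs on 27, 39 or 51 DEX days, against at least 3, 3 and 6 under 6.3. Footnote 5 disagrees with 6.1 and the diaries in every cohort, materially so in cohorts 2 and 3. This affects every patient treated, 11 to 31 by the limits in 11.1.

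The counts assume three DEX courses, as 6.1 and the diaries state, and visits within the printed windows. They also treat the DEX mark at C2D1/C3D1 as an error, because 6.1 and the diaries give no DEX on those days. For cohort 3 they use the 28-day cycle of the Trial Summary and diary; footnote 6 of that calendar prints 21 days. No toxicity rate enters the result, and it does not depend on Figure 1.

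The finding does not extend to the cohort steps in 11.1. A numeric safety limit there is an optional design choice.

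**What to change.** 1. In all three 7.2 schedules, add CBC and metabolic profile to every DEX period, including the first course from Day 0. Place at least one draw in each 9- or 13-day course and two in each 17-day course. In cohort 1 full dosing ends on Day 6, so a mid-course draw leaves the hold more room to act than one on Day 7.
2. Correct both ranges in footnote 5 for each cohort. First course: Days 0–8, 0–12 and 0–16. Later courses, by cycle day: 10–18, 6–18 and 9–25.
3. Remove the DEX mark at C2D1/C3D1. While editing, reconcile the cycle length in footnote 6 of the cohort 3 calendar with the Trial Summary.

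The cost is calendar edits and draws that 6.3 already orders: at least 3, 3 or 6 per patient over three courses. Sample size, stopping rules and analyses do not change.
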